1.2 Secondary Objectives

- Determine changes in the peripheral blood cytokine after REtherapy for primary and secondary malignancies of the liver.
- Determine the changes in infiltrating immune cell within the treated tumor which occur after RE therapy for primary and secondary malignancies of the liver.
- Determine the changes in infiltrating immune cell within non-treated liver tumors which occur after RE therapy for primary and secondary malignancies of the liver.

2 Background and Rationale

The importance of the immune system in the treatment of cancer has been well established over the last several decades, leading to the development of immunotherapies (1). It has also been noted that certain loco-regional therapies such as external beam radiation (XRT) and thermal ablation induce immunologic responses (2-6). However, to date basic research into the immune response induced by RE, a recently established standard of care treatment for primary and secondary malignancies of the liver, is lacking (7,8).

Rarely, loco-regional therapy can induce a positive immune response systemically, termed an abscopal effect. Pre-clinical studies with XRT have suggested that single high dose radiation, not clinically obtainable with XRT, but regularly performed in RE, make abscopal events more frequent (9-11). This suggest RE may be an excellent method of inducing abscopal effects as the deliverable dose to the tumor can be as high as 200-300 Gy, much higher than clinically obtainable by XRT (11). However, despite the apparent potential of RE to positively modulate the immune system and the dramatic benefits this may provide, little research has been performed in this area.

Five prior papers have investigated cytokine changes following RE (12-16). Both Carpizo et al and Lewandowski et al focused on the release of angiogenic factors which have been shown to be tumor protecting, however, are not focused on immunomodulation.

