Patients will undergo biopsy of the largest percutaneous available tumor to be treated within a 12-week period prior to treatment and optionally at 2 weeks (\pm 7 days) following RE. If the pre-treatment biopsy is not standard of care, it will be done for research. The 2-week after treatment biopsy will be performed strictly for research purposes. The optional post RE biopsy will include a treated (defined as a lesion which had y90 delivered to it as determined on standard of care Bremsstrahlung scan after RE) and non-treated lesion (defined as a lesion which did not receive y90 as determined on standard of care Bremsstrahlung scan after RE). Four 18-gauge core needle biopsies will then be obtained. One of the four cores will immediately be placed on ice and sent to our CLIA approved research laboratory. This sample will then be flash frozen and

stored at -80 degrees. Three of the cores will immediately be placed into formalin and submitted to the research laboratory where they will undergo paraffin embedding. These samples will also be stored until analysis can be undertaken. A paraffin embedded sample will then undergo immunohistochemistry analysis. The samples will be analyzed using a standard streptavidin biotinylated alkaline phosphatase method or a streptavidin biotinylated horseradish peroxidase method as described previously (17,18). The slides will then be analyzed using a standard light microscope and CCD-camera at 20x objective. The slides will be scanned into digital format using an Aperio XT scanner (Leica Biosystems Inc. Buffalo Grove, IL). A pathologist will then demarcate the tumor area on the slide. This area of interest will be analyzed using the counting software "FiJI-ImageJ" (FIJI) will be used to quantify the number of infiltrating cells (cell/mm²) in the tumor. They will also be analyzed by the number of infiltrating cells per 100 tumor cells. These analytic standards have been previously described (17,18). The infiltration of immune cells into the tumor before and after treatment will then be compared with each patient serving as their own control.

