9.4 Record Retention

The investigator will retain study records including source data, copies of case report form, consent forms, HIPAA authorizations, and all study correspondence in a secured facility for at least 6 years after the study file is closed with the IRB.

10 Statistical Considerations

Descriptive statistics will be calculated for outcomes and variables of interest. Continuous variables will be summarized using mean and standard deviation, or median and interquartile range, as appropriate. Categorical variables will be summarized using frequencies and percentages. Plots of each peripheral lymphocyte at baseline and each subsequent time of measurement (as stated in the protocol synopsis section) will be generated. This will help determine if individuals have different baseline peripheral lymphocyte values or different peripheral lymphocyte value trends over time. Similar plots will be generated for each cytokine (*IL-1 α* , *IL-1 β* , *IL-2*, *IL-6*, *IL-10*, *IL-12p70*, *IL-18*, *TNF α* , *IFN-Y*, *Fit ligand 3*, and *MCP-1*).

Primary analysis: To determine if there is a change in peripheral lymphocytes following RE, a mixed model with random intercept and random slope for time, and adjustment for baseline peripheral lymphocyte value will be carried out for each lymphocyte. The fixed effect for time, representing the slope over time, will be tested for significance, and a 95% confidence interval will be reported. Depending on if the outcome is skewed, appropriate transformations will be used. Similar models may be carried out with adjustment for certain variables such as age, sex, and size of tumor. Additionally, to investigate specific changes in peripheral lymphocytes from baseline, pairwise comparisons between baseline and each measurement following RE, using paired t-tests or Wilcoxon signed-rank tests, will be performed with a Bonferroni adjustment for multiple comparisons.

Secondary analysis: To determine if there is a change in active cell infiltration into tumors following RE, paired t-tests or nonparametric Wilcoxon signed-rank tests will be used, depending on the distribution of the outcome. These analyses will be performed for the different tumor types (treated and non-treated tumors). In the case that certain variables such as age, sex and size of tumor are of interest, a mixed model will be obtained using an appropriate distribution assumption of the outcome (e.g. Gaussian, Poisson or negative binomial).

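### In treated lesions, infiltrating cells per 100 tumour cells can change after RE with no immune cell entering, and the plan does not say whether this ratio or cells/mm² is the tested measure

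*Combined protocol and SAP*

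**What the plan says.** Section 7.4 describes the slide reading. "A pathologist will then demarcate the tumor area on the slide", and software is then used to "quantify the number of infiltrating cells (cell/mm²) in the tumor". A second scale follows: "They will also be analyzed by the number of infiltrating cells per 100 tumor cells". Both scales are referred to methods in two cited studies of head and neck tumours.

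The comparison is within patient: "The infiltration of immune cells into the tumor before and after treatment will then be compared with each patient serving as their own control". The treated tumour is biopsied before RE and "optionally at 2 weeks (\pm 7 days) following RE".

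Section 10, under secondary analysis, gives the test: "To determine if there is a change in active cell infiltration into tumors following RE, paired t-tests or nonparametric Wilcoxon signed-rank tests will be used". It applies these tests to treated and to non-treated tumours. It does not say whether the tested outcome is cells/mm², cells per 100 tumour cells, or both.

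The protocol text does not define a countable tumour cell, give a rule for necrotic tissue inside the outline, plan to report the tumour-cell count itself, or say what to conclude if the two scales disagree.

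**The concern.** A before/after ratio tracks its numerator only if treatment leaves the denominator alone. Here the denominator is the tumour-cell count, and tumour cells are what RE is given to destroy. Section 2 notes that "the deliverable dose to the tumor can be as high as 200-300 Gy". If tumour cells are lost by the 2-week biopsy and immune cells stay as they were, the ratio rises although nothing has infiltrated.

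At stake is the secondary objective on infiltrating cells in the treated tumour. With no lead scale named, a significant rise in the ratio could be reported as RE-induced infiltration when it reflects only loss of tumour cells. The choice between two scales would also remain open until after the slides are read.

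**Working it through.** The plan gives no expected value, SD or power for infiltration, so there is no figure of its own to reproduce. The check is algebra, then an illustration with assumed inputs.

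**Inputs from the documents.** Two scales on the same outlined area; paired comparison before RE and at 2 weeks ± 7 days (Section 7.4); two-sided tests at 0.05 (Section 10); accrual goal of 30, which caps the number of pairs.

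**Assumed inputs.** t = fraction of counted tumour cells lost; i = fraction of resident immune cells lost; SD of the paired difference in the log ratio. The documents give none of these.

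**Step 1: the ratio with no immune-cell entry.** Start with immune count I and tumour count T. Before RE the ratio is 100 × I/T. After RE it is 100 × I(1 - i)/[T(1 - t)]. Hence

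after/before = (1 - i)/(1 - t).

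**Step 2: no immune-cell loss (i = 0).** Take 200 immune cells and 1000 tumour cells in 2 mm². The starting values are 20 per 100 tumour cells, 100 immune cells/mm² and 500 tumour cells/mm².

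| Assumed t | Multiplier 1/(1 - t) | Per 100 tumour cells | Immune cells/mm², whole outline (2 mm²) | Tumour cells/mm², whole outline |
|---|---|---|---|---|
| 10% | 1.11 | 22.2 | 100 | 450 |
| 30% | 1.43 | 28.6 | 100 | 350 |
| 50% | 2.0 | 40 | 100 | 250 |
| 80% | 5.0 | 100 | 100 | 100 |

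The ratio moves and the whole-outline density does not. The last column shows why: the ratio is 100 × (immune cells/mm²)/(tumour cells/mm²), for example 100 × 100/250 = 40.

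**Step 3: with immune-cell loss.** At t = 50%, i of 25%, 50% and 75% gives 0.75/0.5 = 1.5, 0.5/0.5 = 1.0 and 0.25/0.5 = 0.5. The ratio rises only if t > i, is flat at t = i, and falls if i > t.

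**Step 4: the area matters too.** If the outline is cut back to viable tumour, the area becomes 2 × (1 - t) mm². If all 200 immune cells stay inside it, then at t = 50% density is 200/1 = 200 per mm², up from 100. This is the same artefact on the other scale.

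**Step 5: effect on the test.** For a paired t-test on the log ratio with i = 0, the mean shift is -ln(1 - t): 0.288 at t = 25% and 0.693 at t = 50%. The noncentrality is shift/SD × √n. The chance of a significant result with no immune change, against a nominal 5%, for an assumed SD of 0.5 and then 1.0:

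- 10 pairs: 37% and 13% at t = 25%; 97% and 50% at t = 50%.
- 30 pairs: 86% and 33% at t = 25%; 100% (rounded) and 96% at t = 50%.
- At t = 10% it is smaller: 9% and 6% with 10 pairs; 20% and 9% with 30 pairs.

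**The case against.** The strongest reply is that the plan already has a scale that does not use the tumour-cell count. Cells/mm² comes first in Section 7.4 and the ratio is an addition. That stands: the objective can still be answered, and what is missing is a ranking of the two scales and an area rule. It does not remove the point, because Section 10 leaves either scale open to carry the conclusion.

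The reply is also right that several stronger readings go beyond the documents:

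- A reader might infer that the ratio must rise after RE. Step 3 shows that it need not: resident immune cells in an irradiated lesion may be lost too, and the documents give neither fraction. The dose in Section 2 is an upper figure offered as rationale for abscopal effects, not evidence of cell loss at 2 weeks.
- A reader might infer that the bias favours the trial's hypothesis. The objectives speak of changes and the tests are two-sided; no directional hypothesis is stated.
- A reader might infer that a treated-versus-untreated test is distorted. Section 10 applies the paired tests to each lesion type and sets out no test between them.
- A reader might infer that necrotic tissue is counted in the area. The text neither includes nor excludes it, and the cited methods, which are not available here, may contain a rule. The fair statement is that this document does not specify one.

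Finally, the scale is supplementary, the objective secondary and the post-RE biopsy optional; Section 7.3 ranks the blood-cell changes as scientifically most important. This limits the weight of the point. It does not make the ratio safe to interpret: under the assumptions of Step 5, ten pairs are enough for a misleading result if tumour-cell loss is substantial.

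**Conclusion.** The point holds in a limited form. In treated lesions the ratio per 100 tumour cells can change with no immune-cell entry, by the factor (1 - i)/(1 - t). With i = 0 and assumed t from 10% to 80%, that is a factor of 1.11 to 5.0; with i at or above t, the ratio is flat or falls. All these values rest on assumed t and i, and the test illustration also on an assumed SD, so they show what is possible and are not an estimate of what this trial will see.

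Whole-outline density does not respond to t provided the outlined area is set by the same rule and does not itself shrink. It still reflects the net of immune-cell entry and loss, but a net change is what the objective asks for.

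This is a cheap improvement to a secondary analysis. It does not bear on the primary blood endpoint.

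**What to change.** In Sections 7.4 and 10:

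1. Name immune cells/mm² over one predefined area as the outcome of the paired test. Define the area as the whole tumour outlined by the pathologist, with the same written rule before and after RE, including how necrotic tissue is handled.
2. Keep cells per 100 tumour cells as a descriptive result. Say which tumour cells count, show tumour cells/mm² beside it at both times, and draw no conclusion about infiltration from the ratio alone.
3. If density in viable tumour is also reported, label it a sensitivity result only, because shrinking the area to viable tumour can raise density with no immune entry (Step 4).

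The cost is a few sentences. No new patient, biopsy or assay is needed, and the ratio already requires the tumour-cell count; the optional viable-tumour result would need one further outline on slides already being marked. The wording should be settled before post-RE slides are read. The downside is that the ratio no longer supports the conclusion alone.

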Wickremeskera et al did study changes in several immunomodulating cytokines (IL-1 β , IL-6, IL-8, IL-10, IL12, TNF α , and IFN-Y) however, only did so over the first 48 hours. The half-life of yttrium 90 is 64.1 hours, therefore much of the radiation dose and potentially the immunomodulation, will not have occurred at 48 hours. Fernandez-Ros et al. focused on the induction of liver regeneration following RE and through that studied among other factors the change in IL-6, IL-8, and TNF- α before and at 4 time points following treatment out to 2 months (15). Finally, Seidensticker et al. investigated the prognostic effects of IL-1, IL-2, IL-4, IL-6, IL-8, and TNF- α on overall survival and liver dysfunction with serum blood draws prior to and at 3 days and 6 weeks after radioembolization (16). They found that pre-

treatment IL-6 and IL-8 values portended a worse prognosis (16). These studies have also found that RE leads to modifications in several cytokines (IL-1 and IL-6) (12, 15, 16) however, they do not focus on the immunomodulatory capabilities of these cytokines, include a comprehensive cytokine profile, nor correlate cytokine changes with immune cell infiltration or peripheral lymphocyte changes.

Similarly, while the ability of XRT to induce immune cell infiltration has been investigated (17,18), this has not been documented in RE. Multiple cells including cytotoxic T cells, natural killer cells, helper T cells, dendritic cells, and macrophages have been shown to play roles in immune mediated tumor cell death and tumoral cell protection pathways (17). The infiltration of these cells into a treated tumor following RE is significant in the understanding of how RE induces immune modulation. Recently Chew et al published the first study to investigate immune cell infiltration following RE (19). The demonstrated higher expression of granzyme B and infiltration of CD8⁺ T cells, CD56⁺ NK cells and CD8⁺ CD56⁺ NK cells into treated tumors. They also demonstrate an increase in the TNF- α on both CD8⁺ and CD4⁺ T cells as well as an increase in the percentage of antigen presenting cells after RE.

3 Patient Selection

Study entry is open to patients 22 years of age and older regardless of gender, race, or ethnic background. While there will be every effort to seek out and include minority patients, the patient population is expected to be no different than that of other studies enrolling a similar population at UMN.

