Clinical follow up with magnetic resonance imaging (MRI) or CT will occur at 1 month and 3 months. Radiologic response will be evaluated at 3 months using Response Evaluation Criteria in Solid Tumors (RECIST) and modified RECIST guidelines. Overall survival will be defined as time from RE to death, and patients will be censored for transplantation. Progression free survival will be defined as time from RE to progression as defined by RECIST and mRECIST.

Peripheral blood monocytes will be collected and processed for flow cytometric analyses and cryostorage for later batch studies. The effect RE on lymphocyte repertoire, numbers and phenotype will be assessed at baseline and at defined time points during the trial (7 days (+/- 6 days), 4 weeks (+/- 2 weeks), and 12 weeks (+/- 2 weeks). The frequency and percentage of peripheral blood monocytes and T-cell subsets (CD4 and CD8 effector memory, central memory and Treg subsets), NK cells and myeloid-derived suppressor cells will be determined. Peripheral blood tumor-specific T cell subsets will be evaluated by flow cytometry in cooperation with the Translational Therapy Laboratory, Masonic Cancer Center. Cytotoxic T lymphocytes (CD8+ T cells) and CD4+ helper T cells will be isolated using fluorescence-activated cell sorting (FACS) from cryopreserved cells followed by mRNA expression analysis to assess gene expression changes resulting from therapy. Testing will be performed in the UMN Flow Cytometry and Genomics Core Laboratories. Peripheral blood monocytes may also be tested in functional assays (i.e. IFN- γ ELISpot) for responses to known antigens as well as to predicted neoantigens from whole-exome/transcriptome sequencing of melanoma tumors. All patients will also undergo HLA testing to enable epitope discovery using available MHC binding prediction algorithms.

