On the day of RE patients will have labs drawn, as is consistent with current practice. In addition to standard labs (total bilirubin, international normalized ratio (INR), complete blood count (CBC)) the patients will have an additional tube drawn to be analyzed for cytokine level. To determine the effects on cytokines (*IL-1 α , IL-1 β , IL-2, IL-6, IL-10, IL-12p70, IL-18, TNF α , IFN- γ , Fit ligand 3, and MCP-1*) over a period of time the cytokines will be analyzed following RE at 7 days (+/- 6 days), 4 weeks (+/- 2 weeks) and 12 weeks (+/- 2 weeks). All cytokines will be measured in a similar way through the Cytokine Reference Laboratory at the UMN. This Clinical Laboratory Improvement Amendments (CLIA) approved lab specializes in the analysis of cytokines, chemokines, and growth factors, and as such is very qualified to perform these tests which they have been performing for several years on a regular basis. The tests will be performed in a similar fashion to prior authors (15-17).

The blood cells, blood serum and the biopsy samples will then be stored at the clinical research lab at the University of Minnesota

8 Event Monitoring, Documentation, and Reporting

Toxicity and adverse events will be classified and graded according to NCI's Common Terminology Criteria for Adverse Events version 5.0 (CTCAE V5) and reported on the schedule below. A copy of the CTCAE can be downloaded from the CTEP home page. (http://ctep.cancer.gov/protocolDevelopment/electronic_applications/ctc.htm#ctc_50).

The following definitions of adverse events (AEs) and serious adverse events (SAEs) will determine whether the event requires expedited reporting via the SAE Report Form in addition to routine documentation in the OnCore AE case report form (CRF).

Note: throughout this section the generic term "study drug" refers to the study related procedures.

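### The 7-day blood draw may be taken from day 1 to day 13, so it can fall within 48 hours of radioembolization, and the paired tests pool all such draws as one time point

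*Combined protocol and SAP*

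**What the plan says.** **Window.** The synopsis, the table in Section 7.2 and the text of Section 7.4 agree on the first draw after RE. For cytokines, Section 7.4 says "the cytokines will be analyzed following RE at 7 days (+/- 6 days), 4 weeks (+/- 2 weeks) and 12 weeks (+/- 2 weeks". For lymphocytes it gives the times as "7 days (+/- 6 days), 4 weeks (+/- 2 weeks), and 12 weeks (+/- 2 weeks". The table writes 1 week with the same six-day tolerance for both. Section 7.3 names 7 days without a tolerance. No section sets a minimum interval after RE or says how a very early draw is handled.

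**Rationale.** Section 2 describes an earlier study of immunomodulating cytokines that "only did so over the first 48 hours". It adds that "The half-life of yttrium 90 is 64.1 hours", and "therefore much of the radiation dose and potentially the immunomodulation, will not have occurred at 48 hours".

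**Analysis.** Section 10 fits a mixed model with random intercept and slope to each lymphocyte population: "The fixed effect for time, representing the slope over time, will be tested for significance". It does not say whether time is the nominal visit or the actual day. It then adds "pairwise comparisons between baseline and each measurement following RE, using paired t-tests or Wilcoxon signed-rank tests", with a Bonferroni adjustment. Cytokines are to be analysed in a similar way.

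**Status of the visit.** The synopsis lists 7-day lymphocyte changes as a secondary objective. Section 7.3 lists 7-day changes in peripheral blood cells (called monocytes there) and in cytokines as secondary endpoints.

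**The concern.** Section 2 treats 48 hours as a point at which most of the radiation effect may not yet be visible, but a draw at 24 to 48 hours satisfies the schedule and would not be a deviation. Nothing anchors the draw to day 7. Section 7.2 ties research samples to clinical care where possible, and the only clinical follow-up times the protocol gives are imaging at 1 and 3 months (Section 7.4).

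The paired tests contain no time term. A sample taken the day after the procedure and one taken nearly two weeks later both count as the 7-day value. If the immune profile changes over that interval, the mean 7-day change depends on when patients happened to be sampled. It cannot then be read as the change at about one week.

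**Working it through.** **Inputs**
- First-draw window: 7 days ± 6 days (synopsis, 7.2, 7.4).
- Later windows: 4 weeks ± 2 weeks and 12 weeks ± 2 weeks (same places).
- Half-life: 64.1 hours (Section 2).
- Accrual goal: 30 patients (synopsis, 3.3).

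**Step 1: the windows.**
- First draw: 7 − 6 = day 1 to 7 + 6 = day 13.
- Second draw: 28 − 14 = day 14 to 28 + 14 = day 42.
- Third draw: 84 − 14 = day 70 to 84 + 14 = day 98.

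**Step 2: dose delivered by time t.** The protocol gives no figure to reproduce, only the remark about 48 hours. For physical decay with microspheres that stay in place, fraction delivered = 1 − 2^(−t/64.1), with t in hours.

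| Time after RE | t (h) | Fraction delivered |
|---|---|---|
| Day 1 | 24 | 22.9% |
| Day 2 | 48 | 40.5% |
| Day 3 | 72 | 54.1% |
| Day 7 | 168 | 83.7% |
| Day 13 | 312 | 96.6% |
| Day 14 | 336 | 97.4% |

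At 48 hours, 100 − 40.5 = 59.5% is still to come, so the protocol's remark agrees with its half-life. Across the permitted window the delivered fraction varies by 96.6/22.9 = 4.2-fold. From day 14 on it is at least 97.4%, so the half-life argument does not reach the two later draws.

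**Step 3: how many draws could be early.** The documents give no distribution of draw days. As an illustration, assume an even spread over the window:
- by calendar day, days 1 and 2 out of 13: 2/13 = 15%;
- on a continuous scale from day 1 to day 13: (2 − 1)/(13 − 1) = 1/12 = 8%.

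If all 30 patients gave this sample, that would be 30 × 0.083 = 2.5 to 30 × 0.154 = 4.6 patients.

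**Step 4: which analyses are touched.**
- Baseline versus 7 days, paired: touched, because there is no time term.
- Mixed-model slope: touched if nominal day is used, since a day-1 sample would enter six days from its true position.
- Baseline versus 4 weeks and versus 12 weeks, paired: not touched.

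**The case against.** A reader might infer that the trial repeats the very limitation it was set up to avoid, or that the protocol declares samples within 48 hours uninformative. The documents support neither reading. Section 2 faults a study whose sampling stopped at 48 hours, and it hedges on whether the immune effect is also delayed. This trial samples again at 4 and 12 weeks, and Section 2 gives other reasons for doing it: a fuller cytokine profile, a focus on immunomodulation, and correlation with infiltration and peripheral lymphocytes. Nor is the 12-week comparison, which carries the primary objective in the synopsis, compromised by this window.

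Three further objections deserve weight:
- **The mixed model can use actual draw day.** That is true, and one sentence would settle it. But Section 10 is silent, and the paired tests would still pool the draws.
- **The 4.2-fold range compares the two edges of the window, and cumulative decay is not immune response.** Both stand. The figures show how different the compliant samples may be in delivered dose. They do not measure bias.
- **A narrower window may be hard to schedule.** The protocol names no routine one-week clinical visit, and Section 7.3 reports that the second biopsy was a barrier to enrollment. This argues for the smallest change that meets the 48-hour argument. A later bound, such as day 5, has no source in the documents and would set aside days 3 and 4, to which that argument does not apply.

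**Conclusion.** The point holds as a modest one about a secondary time point. The schedule permits 7-day samples when 23% to 41% of the dose has been delivered, against 84% at day 7 and 97% at day 13, and the paired tests treat them alike. The consequence is confined to the 7-day lymphocyte and cytokine comparisons, plus the slope if it is fitted on nominal day.

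The percentages rest on the stated half-life, physical decay only and microspheres that stay in place. The 8% to 15% share of early draws rests on an even spread that the documents neither support nor contradict. The point concerns what the plan allows; how often it will happen is not known.

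**What to change.** 1. **Window.** In the synopsis, Section 7.2 and Section 7.4, reconcile the window with Section 2 by starting this research draw after 48 hours. One example is 7 days (−4/+6 days), that is day 3 to day 13, when 54% to 97% of the dose has been delivered. This leaves 11 permitted calendar days in place of 13.
2. **Time variable.** In Section 10, state that the date and time of each draw are recorded and that actual days since RE are the time variable in the lymphocyte and cytokine mixed models. This also places the later draws correctly, where the tolerance is two weeks.
3. **Early draws.** In Section 10, state that samples taken at or before 48 hours, including any already collected, are reported separately as an acute time point and left out of the 7-day paired comparison. They can stay in the mixed models at their actual day.

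The cost is a short amendment, slightly less scheduling freedom for one blood draw, and possibly a few pairs lost from the 7-day test. Under the even-spread assumption, the loss is about 2 to 5 of 30 if the current window had applied throughout. No new patients or assays are needed.
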